Recent studies link ER stress to the pathogenesis of IBD. Patients with active Crohn's disease and ulcerative colitis exhibit signs of ER stress in their ileal and/or colonic epithelium⁷⁻⁹. In addition, human genetic studies of IBD have identified primary genetic abnormalities in several genes including *XBP1*, *AGR2*, and *ORMDL3* that encode proteins associated with ER stress^{1, 10-13}. Previous studies indicate that cells with a high load of protein folding and secretion are sensitive to altered ER homeostasis and this can induce inflammatory response gene expression^{1, 2, 5, 14, 15}. Intestinal microbiota and their molecules stimulate IECs to increase secretion of mucins and antimicrobial peptides that can overwhelm the protein secretory capacity of IECs. Conversely, exposure to inflammatory stimuli can cause ER stress¹⁵. Upon exposure to high levels of exogenous antigens and inflammatory cytokines in the intestinal lumen, IECs may require efficient UPR-mediated ER chaperone induction to survive the heavy burden of protein folding and secretion.

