2.1 General Design

Figure 1. Trial schema

Type of Study: Open-label clinical trial where all patients receive TUDCA at 1.75 or 2g/day for 6 weeks, divided into three doses, after meals.

Schematic of Trial Design: A total of 12 individuals with active ulcerative colitis and endoscopic evidence of inflammation will be eligible to participate in this open-label clinical trial using TUDCA (adjunct or primary therapy) at 1.75 or 2g/day for 6 weeks, divided into three doses, after meals as summarized in Figure 1. A full schedule of visit assessments and procedures is defined in Table 1 in Section 5.

Duration of Subject Participation: 6 weeks on Trial + 2 weeks Follow up = 8 weeks.

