BIP, XBP1 splicing, phosphorylated eIF2 α will be assessed by Western blot and RT-PCR and immunohistochemistry (IHC). Other ER stress markers, such as PERK, ATF4, CHOP, IRE1 α and ATF6 α will also be examined. In addition, we expect that cell death markers in colon biopsy tissues will also be downregulated, including cJUN, JNK, cleaved caspase 2 and cleaved caspase 3. We will also monitor expression of inflammatory cytokines, IL-1B, TNF α , IL-6 and IFN γ . Additional samples aliquots will be saved (flash frozen and RNAlater) for future studies evaluating adaptive and innate immune readouts.

[name], the co-PI of this study, has a broad background in ER stress and cell death, and discovered the therapeutic role of TUDCA in IBD mouse models with support from CCFA. His laboratory has extensive experience in evaluation of ER stress, inflammation and cell death markers by western-blotting, PCR and IHC in both mouse models and human samples. All the colon biopsy samples will be sent under dry ice for analysis by [name] laboratory. [name], a Research Associate in [name] laboratory will be responsible for analyzing and processing data from the clinical samples.

Significance of primary outcomes: Changes in ER stress markers will clarify the mechanisms through which TUDCA may act to alleviate inflammation in colon tissue of subjects with UC.

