We anticipate that TUDCA therapy will reduce ER stress and promote mucosal healing. As TUDCA has the potential to increase stool frequency, it is important to measure efficacy through objective measures (endoscopy and histology) as well as clinical symptoms. Thus, we will obtain a complete Mayo UC score at weeks 0 and 6 and a partial (no endoscopic subscore) at weeks 2 and 4.32 Biopsies will be obtained at both

endoscopic procedures and objectively scored by the Goebes index. Thus, secondary endpoints will include the following using FDA recommended UC Clinical trial guidelines⁴¹:

- 1) Mucosal Healing: A decrease of at least 1 point on the Mayo endoscopic subscore with a final score of 0 or 1 will be used as a marker of mucosal healing.
- 2) Clinical Response: A decrease in Mayo Score of ≥ 3 points and a decrease in Mayo Score of ≥ 30% from baseline and a decrease in the rectal bleeding score of ≥ 1 or an absolute rectal bleeding score of 0-1.
 - a. Clinical Remission will also be recorded if achieved as defined by a total Mayo Score of ≤2 with no subscore >1 and improvement of endoscopic appearance of the mucosa (Mayo 0 or 1).
- **3) Histologic activity:** *Histologic disease activity.* Colon biopsy samples will be harvested and fixed as described. H&E stained sections will be evaluated for tissue damage and inflammation by a gastrointestinal pathologist in a double-blinded manner, using the simplified Geboes histology index^{34, 35}

We expect that TUDCA treatment will significantly alleviate inflammation in colon tissues, which will be correlated with increased plasma concentration of TUDCA or the deconjugated form UDCA. We will collect stool samples both before and after TUDCA treatment for potential (longer range) studies of gut microbiota composition.

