Data analysis, interpretation and alternative plans: We expect that there will be minimal adverse effects due to TUDCA treatment, as its safety in humans has been proven in clinical trials for other disease conditions. We expect that TUDCA treatment will improve endoscopic and histologic parameters of inflammation. We also anticipate that it will improve overall Mayo scores and lead to clinical response, if not remission. It is possible though that TUDCA will exacerbate diarrhea in UC patients and clinical symptoms may worsen even if mucosal healing occurs. It is possible that we will not achieve significant improvement in the severity of inflammation, as mucosal healing can take as long as several months (Lialda induction trial) and our TUDCA treatment duration is only 6 weeks. In this case, we will analyze whether expression of ER stress, inflammation and cell death markers in colon biopsy tissues is correlated with the plasma concentration of TUDCA and its metabolites, which will provide a reliable indication for long-term mucosal healing.

7 Safety and Adverse Events

As Safety and tolerability are secondary endpoints, they are further described above in section 6.

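### The fallback marker–plasma correlation cannot indicate long-term mucosal healing, because the trial measures no long-term healing outcome

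*Combined protocol and SAP*

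**What the plan says.** The last paragraph of Section 6.2 (data analysis, interpretation and alternative plans) allows that the severity of inflammation may not improve significantly. The reason given is that "mucosal healing can take as long as several months (Lialda induction trial) and our TUDCA treatment duration is only 6 weeks". For that event the investigators plan a fallback analysis, which asks if "expression of ER stress, inflammation and cell death markers in colon biopsy tissues is correlated with the plasma concentration of TUDCA and its metabolites". Of that result the plan then makes this claim: "which will provide a reliable indication for long-term mucosal healing".

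Other parts of the protocol fix what will be observed:

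- Section 2.1: "Duration of Subject Participation: 6 weeks on Trial + 2 weeks Follow up = 8 weeks".
- Table 1 (Section 5) and Section 6.2: endoscopy and the full Mayo score at weeks 0 and 6 only. The week 8 contact is a phone call with a partial Mayo score, which has no endoscopic component.
- Section 6.2: mucosal healing is defined by the Mayo endoscopic subscore (a fall of at least 1 point, ending at 0 or 1).
- Section 5, additional analysis on samples: blood for bile acids at the start of TUDCA, at week 2 and at the endoscopic evaluation.
- Section 6.1: 12 patients enrolled. The only sample-size calculation is for the before/after change in three ER stress markers.

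For this fallback the plan names no coefficient, principal marker, time point, precision target or multiplicity rule.

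**The concern.** The plan states in advance a favourable long-term conclusion that comes into play only when the trial has failed to show improved inflammation. The conclusion is worded as something the analysis will deliver, not something it might suggest. A reader of the eventual report could take a correlation between drug level and a tissue marker as evidence that patients will heal later, although no patient is examined endoscopically after week 6. Because no single correlation is chosen from a large set, a chance finding could fill that role.

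**Working it through.** **1. Does the conclusion follow from the variables?** One side of the correlation is a tissue marker. The other is the plasma concentration of the drug or a metabolite. Healing, as Section 6.2 defines it, is on neither side. The last endoscopy is at week 6 and the last contact at week 8, while the paragraph's own time scale for healing is months. Nothing in the document gives evidence that a marker–plasma correlation predicts later healing. So r = 1 would show that exposure and the marker move together, and no more. This holds at any sample size.

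**2. What does the plan's sample size cover?** Table 2 gives 5.09 (power 0.8) and 6.39 (power 0.9), from which the text takes 7 patients. With standardised difference 0.52/0.26 = 2.0 and two-sided alpha 0.05, a two-sample t-test calculation (noncentral t) returns 5.09 and 6.39 per group, an exact match. Whether those inputs suit a before/after comparison is a separate matter. Here the point is that the figures concern a difference in means and say nothing about a correlation.

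**3. Precision of a correlation.** The plan names no coefficient; Pearson's r with bivariate normal data is assumed here.

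95% CI = tanh(atanh(r) ± 1.96/√(n−3)); atanh(0.6) = 0.693.

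- n = 12: 1.96/√9 = 0.653. Limits tanh(0.040) = 0.04 and tanh(1.346) = 0.87.
- n = 7: 1.96/√4 = 0.98. Limits tanh(−0.287) = −0.28 and tanh(1.673) = 0.93.

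Smallest |r| reaching two-sided 0.05 = t/√(n−2+t²): 0.576 at n = 12 and 0.754 at n = 7.

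Power, from 200,000 simulated samples per setting:

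| True r | n = 12 | n = 7 |
|---|---|---|
| 0.3 | 16% | 10% |
| 0.5 | 40% | 21% |
| 0.7 | 78% | 46% |
| 0.8 | 93% | 67% |

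By the Fisher approximation, n = ((1.96+0.8416)/atanh(r))² + 3, 80% power needs 30 patients at r = 0.5 and 14 at r = 0.7.

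Twelve is the enrolment, so it is the most that can contribute. Seven evaluable is an assumption: it is the number Section 6.1 calls sufficient for the primary comparison, and reaching it would mean losing 5 of 12 (42%).

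**4. Number of possible correlations.** Section 6 names 3 primary markers, 5 other ER stress markers, 4 cell-death markers and 4 cytokines: 16 in all. Section 6.2 names TUDCA and its deconjugated form UDCA as plasma analytes, giving 16 × 2 = 32 pairs at a single time point.

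If every pair is tested at 0.05, with no true associations:

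- 16 tests: expected false positives 16 × 0.05 = 0.8. If independent, P(at least one) = 1 − 0.95¹⁶ = 56%.
- 32 tests: expected 32 × 0.05 = 1.6. If independent, P(at least one) = 1 − 0.95³² = 81%.

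Dependence between tests would lower both probabilities but not the expected counts.

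**The case against.** This is one sentence under alternative plans in an open-label, single-arm Phase I study. Efficacy is a secondary endpoint to be reported qualitatively, and no success criterion, sample size or stopping rule depends on the correlation. That stands, and it limits the size of the point. It does not supply a basis for the long-term claim.

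A reader might infer that 12 patients cannot estimate a correlation at all. They can: power is 78% at a true r of 0.7 and 93% at 0.8. What they cannot do is estimate a weak or moderate correlation with useful precision.

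The less favourable figures depend on assumptions. The plan does not say that 7 patients will be evaluable; its dropout sentence breaks off in the available text. Independence is close to a worst case, since UDCA derives from TUDCA and several markers belong to the same stress-response branches. The 0.05 threshold is stated for the primary comparison, not for this analysis.

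It is also tempting to treat the Section 6 sentence "Changes in ER stress markers will clarify the mechanisms through which TUDCA may act" as a second overclaim, given the background remark "Conversely, exposure to inflammatory stimuli can cause ER stress". The documents do not carry that far. The sentence is hedged by its own verb, the background says only that inflammation can cause ER stress, and the fallback applies when inflammation has not significantly improved, which weakens the argument that a marker fall merely follows reduced inflammation. Changing that sentence is mainly a wording preference and is not part of this point.

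Finally, some useful context is already planned: biopsies of non-inflamed colon where available, and correlation of primary with secondary endpoints. What is missing is a single pre-named pair and an interval.

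**Conclusion.** The point holds. The long-term healing inference is wrong as written, from the design alone and without any numerical assumption. The calculations add that the estimate would not be reliable in the ordinary sense either. At full enrolment, an observed r of 0.6 is compatible with anything from almost no association to a very strong one; with 7 evaluable patients, the interval would include zero. The 56% and 81% false-positive figures are upper illustrations that require all pairs to be tested at 0.05 and to be independent.

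A reader might go further and infer that the fallback could reverse the trial's result. The documents do not support that, because no decision rule uses it. The fault is confined to what the trial may say after a null efficacy result.

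**What to change.** In the last paragraph of Section 6.2:

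- Delete the clause on long-term mucosal healing.
- State that the correlation is exploratory and hypothesis-generating, and that it cannot offset a null efficacy result.
- Name one marker, one analyte and one time point in advance (for example, change in one of the three primary markers against fasting week 6 plasma TUDCA), with the coefficient, and report it with a 95% CI and the number of patients contributing.
- Report how many other correlations were examined and label them exploratory.

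The cost is a few sentences. The blood and biopsies are already scheduled, so no visit or sample is added. The downside is that the stated conclusion becomes weaker.

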7.1 Definitions

Adverse Event

An **adverse event** (AE) is any symptom, sign, illness or experience that develops or worsens in severity during the course of the study. Intercurrent illnesses or injuries will be regarded as adverse events. Abnormal results of diagnostic procedures are considered to be adverse events if the abnormality:

- results in study withdrawal
- is associated with a serious adverse event
- is associated with clinical signs or symptoms
- leads to additional treatment or to further diagnostic tests
- is considered by the investigator to be of clinical significance

Serious Adverse Event

Adverse events are classified as serious or non-serious. A **serious adverse event** is any AE that is:

- fatal
- life-threatening
- requires or prolongs hospital stay
- · results in persistent or significant disability or incapacity
- a congenital anomaly or birth defect
- an important medical event

What are serious adverse events or unanticipated problems?

Any incident, experience, or outcome that meets all of the following criteria:

- (1) unexpected (in terms of nature, severity, or frequency) given (a) the research procedures that are described in the protocol-related documents, such as the IRB-approved research protocol and informed consent document; and (b) the characteristics of the subject population being studied;
- (2) related or possibly related to participation in the research (in this guidance document, possibly related means there is a reasonable possibility that the incident, experience, or outcome may have been caused by the procedures involved in the research);
- (3) and suggests that the research places subjects or others at a greater risk of harm (including physical, psychological, economic, or social harm) than was previously known or recognized.

All adverse events that do not meet any of the criteria for serious should be regarded as **non-serious adverse events**.

Adverse Event Reporting Period

The study period during which adverse events must be reported is normally defined as the period from the initiation of any study procedures to the end of the study treatment follow-up. For this study, the study treatment follow-up is defined as 14 days following the last administration of study treatment.

Preexisting Condition

A preexisting condition is one that is present at the start of the study. A preexisting condition should be recorded as an adverse event if the frequency, intensity, or the character of the condition worsens during the study period.

General Physical Examination Findings

At screening, any clinically significant abnormality should be recorded as a preexisting condition. At the end of the study, any new clinically significant findings/abnormalities that meet the definition of an adverse event must also be recorded and documented as an adverse event.

Post-study Adverse Event

All unresolved adverse events should be followed by the investigator until the events are resolved, the subject is lost to follow-up, or the adverse event is otherwise explained. At the last scheduled visit, the investigator should instruct each subject to report any subsequent event(s) that the subject, or the subject's personal physician, believes might reasonably be related to participation in this study. The investigator should notify the study sponsor of any death or adverse event occurring at any time after a subject has discontinued or terminated study participation that may reasonably be related to this study. The sponsor should also be notified if the investigator should become aware of the development of cancer or of a congenital anomaly in a subsequently conceived offspring of a subject that has participated in this study.

Abnormal Laboratory Values

A clinical laboratory abnormality should be documented as an adverse event if any one of the following conditions is met:

- The laboratory abnormality is not otherwise refuted by a repeat test to confirm the abnormality
- The abnormality suggests a disease and/or organ toxicity
- The abnormality is of a degree that requires active management; e.g. change of dose, discontinuation of the drug, more frequent follow-up assessments, further diagnostic investigation, etc.

Hospitalization, Prolonged Hospitalization or Surgery

Any adverse event that results in hospitalization or prolonged hospitalization should be documented and reported as a serious adverse event unless specifically instructed otherwise in this protocol. Any condition responsible for surgery should be documented as an adverse event if the condition meets the criteria for and adverse event.

Neither the condition, hospitalization, prolonged hospitalization, nor surgery are reported as an adverse event in the following circumstances:

 Hospitalization or prolonged hospitalization for diagnostic or elective surgical procedures for a preexisting condition. Surgery should *not* be reported as an outcome of an adverse event if the purpose of the surgery was elective or diagnostic and the outcome was uneventful.

- Hospitalization or prolonged hospitalization required to allow efficacy measurement for the study.
- Hospitalization or prolonged hospitalization for therapy of the target disease
 of the study, unless it is a worsening or increase in frequency of hospital
 admissions as judged by the clinical investigator.

7.2 Recording of Adverse Events

At each contact with the subject, the investigative team must seek information on adverse events by specific questioning and, as appropriate, by examination. Information on all adverse events should be recorded immediately in the source document, and also in the appropriate adverse event module of the case report form (CRF). All clearly related signs, symptoms, and abnormal diagnostic procedures results should recorded in the source document, though should be grouped under one diagnosis.

All adverse events occurring during the study period must be recorded. The clinical course of each event should be followed until resolution, stabilization, or until it has been determined that the study treatment or participation is not the cause. Serious adverse events that are still ongoing at the end of the study period must be followed up to determine the final outcome. Any serious adverse event that occurs after the study period and is considered to be possibly related to the study treatment or study participation should be recorded and reported immediately.

7.3 Reporting of Serious Adverse Events

7.3.1 IRB Notification by Investigator

Reports of all serious adverse events or unanticipated problems (including followup information) must be submitted to the IRB within 10 working days. Copies of each report and documentation of IRB notification and receipt will be kept in the Clinical Investigator's binder.

7.3.2 FDA Notification by Sponsor

The study sponsor shall notify the FDA by telephone or by facsimile transmission of any unexpected fatal or life-threatening experience associated with the use of the drug as soon as possible but no later than 7 calendar days from the sponsor's original receipt of the information.

If a previous adverse event that was not initially deemed reportable is later found to fit the criteria for reporting, the study sponsor will submit the adverse event in a written report to the FDA as soon as possible, but no later than 15 calendar days from the time the determination is made.

7.4 Stopping Rules

Individual stoppage criteria-

Based on extensive clinical trial data, we anticipate that TUDCA will be well tolerated. However, patients will be monitored via study visits and phone calls and will permanently discontinue study drug for any adverse event possibly or probably related to study drug that is considered of *moderate or severe intensity*. To define intensity, we will utilize a standard severity rating scale to ensure this safety monitoring plan is enforced in a standardized fashion. Individual subjects should be discontinued for any adverse event rated a Grade 3 or greater in severity on the Common Terminology Criteria for Adverse Events (CTCAE_v5.0 November 2017) scale v, unless it is clearly related to the underlying disease.

For disease specific symptoms (e.g. diarrhea, rectal bleeding) we will consider disease worsening as an increase in >3 points on the Mayo Score to be potentially related to TUDCA and will lower the dose to 1000 mg as described. If symptoms persist or worsen over the subsequent 5 days, the patient will be permanently discontinued from the study.

Study stoppage criteria-

Enrollment of new subjects should be interrupted should 2 or more patients experience CTCAE Grade 3 event, or 1 or more patients experience CTCAE Grade 4 events not clearly related to the underlying disease. Study enrollment may be resumed following review of all available safety data by the investigator and study team and a concurrent opinion that the totality of the data suggests this event is unlikely to be related to TUDCA. The study should be terminated if, following the review of the safety data, it has not been possible to demonstrate that the adverse event has a clear relationship to the underlying disease or associated co-morbidity.

We will initiate early study termination or enroll all future patients at the 1000 mg dose. This decision will be made with the guidance of the appointed Data Safety and Monitoring Committee. Individual and study stoppage criteria should be applied to these patients as well.

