6.2 Secondary Endpoint Analyses

As this is an open label, Phase I study, secondary endpoints of safety and tolerability will be reported qualitatively. Efficacy will be measured and reported qualitatively by change in Mayo Score, Goebes Histology Index and SIBDQ. As appropriate Student's t test, Mann Whitney U or ANOVA will be used to compare between time points.

1. Active monitoring of UC study patients for TUDCA safety and tolerability

TUDCA has a strong record of safety in several patient populations^{19, 20, 30} (See Detailed Safety Data Review below). However, TUDCA has not been examined specifically in a UC population. Therefore, we aim to define its safety/tolerability in this population through frequent monitoring and symptom assessment as detailed in the study procedures. Adverse events will be categorized according to CTCAE v5.0 criteria and grading.

Infrequent side effects of TUDCA therapy include diarrhea and headache. Our study nurse coordinator will contact all study patients biweekly to assess for any experienced

adverse events. Additionally, in line with WUSM Center for Clinical Trials protocols, patients will have 24 hour access to report suspected Adverse Events. All adverse events or serious adverse events will be recorded and reviewed with treating physician as well as PI. In the event that patients experience an adverse event potentially related to TUDCA, the patient will be offered the option of dose de-escalation or study withdrawal.

TUDCA dose de-escalation strategy: In the setting of a toxicity that the treating physician determines most likely related to TUDCA, we will reduce the dose to 1000 mg (42-50% of initial dose). Common side effects are diarrhea and headache. Since diarrhea is already a symptom implicit to inclusion, we will consider an increase of ≥3 bowel movements/day to be a likely drug toxicity.

Early stopping rules and Dosage Reduction: In the event that ≥50% of patients experience a TUDCA associated side effect or intolerance, we will initiate early study termination or enroll all future patients at the 1000 mg dose. This decision will be made with the guidance of the appointed Data Safety and Monitoring Committee. Full Stopping rules are described in Section 7.4. Note, individual and study stoppage criteria should be applied to these patients as well.

2. Active Monitoring and Management of new elevations in liver transaminases:

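### For a severe non-hepatic event judged most likely due to TUDCA, Section 6.2 reduces the dose where Section 7.4 permanently stops the drug, and no text says which governs

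*Combined protocol and SAP*

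**What the plan says.** Section 6.2, item 1, has two sentences on what to do for an individual patient. The first covers "an adverse event potentially related to TUDCA, the patient will be offered the option of dose de-escalation or study withdrawal". The second sets the reduced dose: "In the setting of a toxicity that the treating physician determines most likely related to TUDCA, we will reduce the dose to 1000 mg", which it describes as 42-50% of the initial dose. Neither mentions severity. The same paragraph adds "Common side effects are diarrhea and headache" and, for diarrhea, "we will consider an increase of ≥3 bowel movements/day to be a likely drug toxicity".

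Section 7.4, under individual stoppage criteria, says that patients "will permanently discontinue study drug for any adverse event possibly or probably related to study drug that is considered of *moderate or severe intensity". It continues "To define intensity, we will utilize a standard severity rating scale" and then stops individual subjects at CTCAE Grade 3 or greater, unless the event is clearly due to the underlying disease. Its only individual dose-reduction route is for disease-specific symptoms. A Mayo rise of more than 3 points lowers the dose to 1000 mg, and the patient is discontinued if symptoms persist or worsen over the next 5 days.

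The sections point at each other. Section 6.2 says "Full Stopping rules are described in Section 7.4", in its paragraph on study-level early stopping. Section 7 opens with "As Safety and tolerability are secondary endpoints, they are further described above in section 6". Section 4.8.4 treats anyone who stops study drug as withdrawn from the study.

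**The concern.** An event judged most likely related to TUDCA is also at least possibly or probably related, so one event can fall under both rules. If it is severe, 6.2 allows treatment to continue at a lower dose, while 7.4 ends treatment for good. These are two stated safety rules that cannot both be followed.

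Two things are at stake. A patient with a severe drug-related event could stay on study drug against the trial's own stopping rule. The same event could also be recorded as a dose reduction under 6.2 or, through 4.8.4, as a study withdrawal. Tolerability is a secondary endpoint in a trial of 12 patients, and the report to the safety committee (7.5.1) must count participants who met the early stopping rules.

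**Working it through.** **1. The rules side by side**, for a non-hepatic event that is judged most likely due to TUDCA and is not handled by the disease-symptom rule in 7.4:

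| Intensity | 6.2 | 7.4, intensity sentence | 7.4, Grade 3 sentence | Result |
|---|---|---|---|---|
| Below moderate | Reduce, or offer reduction or withdrawal | No stop | No stop | Compatible |
| Moderate, below Grade 3 | Same | Permanent stop | No stop | Depends on how 7.4 is read |
| Severe, Grade 3 or greater | Same | Permanent stop | Stop | Direct conflict |

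The disease exception in the Grade 3 sentence does not help in the last row, because the event has been attributed to the drug. A severe drug-related headache, one of the side effects 6.2 names, is an example. The middle row stays open because 7.4 never assigns a CTCAE grade to moderate.

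**2. Does any text rank the sections?** The pointer from 6.2 to 7.4 sits in the paragraph about 50% or more of patients having a side effect. The note that individual and study stoppage criteria also apply to these patients appears in both sections. Each time it follows the option of enrolling future patients at 1000 mg, so those are the patients it most naturally means. The return pointer at the start of Section 7 says only where safety is described. None of these sets an order of precedence.

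**3. Diarrhea.** At least 3 extra bowel movements a day (6.2) and a Mayo rise above 3 (7.4) both lead to 1000 mg. If both are met, 7.4 adds a 5-day review on which 6.2 is silent, so both can be followed. If only the bowel-movement trigger is met, the 5-day review does not apply. A conflict arises only when drug-attributed diarrhea also meets the general stopping rule in 7.4.

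**4. Extra exposure.** Inputs: 6 weeks of treatment (42 days), contacts at weeks 2 and 4 (Table 1), reduced dose 1000 mg a day.

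- Acted on at week 2: 42 - 14 = 28 days; 28 x 1000 mg = 28 g under 6.2, against 0 under 7.4.
- Acted on at week 4: 42 - 28 = 14 days; 14 x 1000 mg = 14 g, against 0.

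**5. The dose percentage in 6.2.** The plan states 42-50% of the initial dose. Starting doses are 1750 mg and 2000 mg.

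- Remaining dose: 1000/1750 = 57.1%; 1000/2000 = 50.0%.
- Reduction: 750/1750 = 42.9%; 1000/2000 = 50.0%.

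The stated range is close to the size of the reduction and is labelled as the remaining dose.

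**The case against.** The best defence is that the sections divide the work: 6.2 gives the de-escalation dose and 7.4 decides when to stop. Section 6.2 names 7.4 as the home of the full stopping rules, 7.4 refers back to the reduction as already described, and the note on stoppage criteria suggests that being on 1000 mg does not displace them. A careful investigator might well act this way. It is a sensible guess at intent, but no sentence applies it to a patient already on treatment.

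A reader might infer that 6.2 forces a patient with a severe event to stay on drug. The documents do not support that. The preceding sentence in 6.2 offers withdrawal as an alternative, and a most likely related event is also a potentially related one. Sections 3.4.1 and 4.8.5 also permit withdrawal for an adverse reaction or event. What stands is that an option to continue at 1000 mg is still incompatible with a required permanent stop.

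A reader might also set 28 days of continued dosing for diarrhea under 6.2 against 5 days under 7.4. That comparison fails, because the two triggers either combine or do not both apply.

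Nor does 6.2 lack severity limits altogether. Its item 2 sets discontinuation thresholds for liver tests, so the point is confined to non-hepatic events.

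Finally, every adverse event is recorded and CTCAE-graded whatever action follows, tolerability is reported qualitatively, and stopping rules are reviewed weekly (9.1). These make a harmful outcome less likely, but they do not tell the team which rule to apply.

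**Conclusion.** The concern holds. For severe, non-hepatic, drug-attributed events, 6.2 and 7.4 give incompatible instructions and the plan does not rank them. For moderate events the conflict exists only if moderate is a stopping level in its own right, which 7.4 leaves unclear. Counting the conflict as a share of severity levels would go too far, because the documents define no such scale.

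The size per affected patient is up to 28 days (28 g) at 1000 mg from the week-2 contact, or 14 days (14 g) from week 4, against none under 7.4. This assumes that the team follows 6.2, that the patient does not choose withdrawal, and that the full 6 weeks are completed. The documents give no rate for such events and describe side effects as infrequent, chiefly mild diarrhea, so no probability can be attached. The effect is on individual safety handling and the consistency of tolerability reporting; the material gives no ground for extending it to the primary analysis. The percentage slip is real but separate and minor.

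**What to change.** 1. Add to 6.2 that dose reduction applies only to related events that do not meet the individual stopping criteria in 7.4, apart from the disease-symptom rule in 7.4, and that 7.4 governs where both could apply.
2. State in 7.4 the CTCAE grade at which a related event stops the drug. If Grade 3 is intended, remove moderate from the intensity sentence; if moderate events should also stop the drug, name their grade.
3. In 6.2, correct the reduced dose to 50-57% of the initial dose (a 43-50% reduction).

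The cost is a wording amendment, with no new visits, samples or patients.
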